### **5.3.2. Binary Endpoints**

For binary secondary endpoints in double-blind phase, intercurrent event will be handled as described in [Section 2.3.2.1](#) (Estimand 2) or [Section 2.3.4](#) (Estimand 6). After the intercurrent event is handled as appropriate, any remaining missing responses will be handled by setting the response value to nonresponsive for visits up to DB Week 52. This method of handling missing responses is known as missing response as non-response (MR=NR).

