The Sponsor will use external Centralized Coordinating Centers to review and confirm applicable real-time assessments of efficacy, including the Adapted JIA ACR 30/50 response, sJIA flare, and inactive disease status (JIA-ACR). The Coordinating Centers will also monitor and offer recommendations on corticosteroid tapering of study participants. The Centralized Coordinating Centers will be blinded to study drug assignment in the double-blind withdrawal phase of the study.

All subjects participating in this study, including those who discontinued in the open-label or double-blind phase, will have the option, if eligible (based on inclusion and exclusion criteria), of enrolling in the tofacitinib JIA long-term extension study (A3921145) after completion of this study.

[figure not shown]
Subjects who flare in the double-blind withdrawal phase will be given the opportunity to participate in A3921145 and be treated with open-label tofacitinib. Subjects who achieve ACR clinical remission (ie, maintain JIA ACR inactive disease during 24 consecutive weeks in the double-blind withdrawal phase) will complete their participation in A3921165 and be given the opportunity to enter A3921145.

Subjects who discontinue investigational product in the double-blind phase and who do not enter A3921145 will continue in A3921165 for follow up of efficacy and safety endpoints.

Subjects will be required to perform all scheduled visits until Week 52 after randomization or until the study concludes, whichever comes first. Subjects should receive standard-of-care treatment in accordance with local treatment guidelines.

Subjects who discontinue the study in the Open-Label Phase and do not enter A3921145, will be required to perform a follow-up visit 28 days after the last dose of investigational product.

A schematic of the study design is shown below:

a Subjects <40 kg will receive an equivalent weight-based lower dose of tofacitinib 5 mg BID.

b CS Tapering is only required for subjects treated with CS >0.2 mg/kg/day oral prednisone (or equivalent). During the active CS tapering period in Part 2 subjects must maintain an Adapted JIA ACR50 response.

c aJIA: Adapted JIA.

d Subjects who discontinue investigational product in the randomized withdrawal phase continue in study until Week 52 after randomization, or until the study concludes, whichever comes first.

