#### 2.3.2.1. Binary Secondary Endpoints in Double-Blind Phase

For binary endpoints such as adapted JIA ACR 30/50/70/90/100 response at each double-blind phase visit, the estimand also uses composite strategy (Estimand 2) and includes the following 5 attributes:

- Population: sJIA patients, as defined by the inclusion criteria for the double-blind phase, who are randomized.
- Treatment: tofacitinib 5 mg BID, placebo

- Variable: binary endpoints such as aJIA ACR 30/50/70/90/100 response at each double-blind phase visit through Week 52.

Patients who complete study participation after maintaining JIA ACR inactive disease for at least 24 weeks (clinical remission) in the double-blind phase, and patients who are still active in the double-blind withdrawal phase of the study but have to discontinue before Week 52 due to study end, will use the last on-treatment windowed visit ([Appendix 3.13](#)) ACR value (ie, last observation carried forward (LOCF)), from that visit onward until Week 52 visit.

Patients who discontinue from the investigational product for any other reasons before Week 52 are considered as treatment failure, ie, ACR non-responders, from that visit onward until Week 52 visit. If there is an on-treatment ACR assessment that falls within the same windowed visit with the investigational product discontinuation, the ACR assessment will prevail.

- Intercurrent event: investigational product discontinuation will be the intercurrent event. The intercurrent event is captured through the variable definition. Data collected after discontinuation of the investigational product (ie, off-treatment data) will not be included to derive the endpoint, ie, only on-treatment data ([Appendix 3.13](#)) collected prior to or at Week 52 visit will be used.
- Population-level summary: difference in proportion of subjects achieving binary endpoint response such as aJIA ACR 30/50/70/90/100 response at each double-blind phase visit through Week 52 between those assigned to tofacitinib at randomization versus those assigned to placebo at randomization.

Estimands for all other binary secondary endpoints except occurrence of disease flares in double-blind phase will follow the same composite strategy as the above secondary estimand. See endpoint definitions in [Section 3.2.1](#) and [Appendix 1](#) and missing data handling in [Section 5.3](#) for specific differences.

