### 2.3.3. Additional Estimands for Primary Endpoint

A supplementary (Estimand 4) estimand for the primary endpoint will use the hypothetical strategy, which estimates the treatment effect if all patients adhere to the protocol and the intercurrent event of investigational product discontinuation has not occurred. It differs from the primary estimand in the following 2 attributes:

- Variable: time to sJIA disease flare in the double-blind phase.

Patients who discontinue from investigational product for reasons other than flare in the double-blind phase and who complete study participation after achieving clinical remission, will be considered as non-flare and censored at the last available flare assessment while on investigational product. (More details of on-treatment censoring time and risk period are provided in [Section 5.3.1.1](#).)
- Intercurrent event: all data after an intercurrent event (investigational product discontinuation), if collected, will be excluded.

A second supplementary estimand (Estimand 5) for the primary endpoint will use the treatment policy strategy and estimate the treatment difference regardless of whether an intercurrent event occurs. It differs from the primary estimand in the following 2 attributes:

- Variable: time to sJIA disease flare in the double-blind phase.

- Intercurrent event: investigational product discontinuation is not considered for analysis. All the flare data collected both on-treatment and off-treatment in the double-blind phase of Study A3921165 will be used. For subjects who withdraw from study early, before reaching 52 weeks of double-blind treatment from Study A3921165 and enrolled in the LTE (Study A3921145), the flare data collected through Week 52 post randomization from both studies A3921165 and A3921145 will be included (see [Section 6.1.2.1](#)). (More details of on-study censoring time and risk period are provided in [Section 5.3.1.1](#).)

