#### 2.3.4. Additional Estimands for Selected Secondary Endpoints

For aJIA ACR 30/50/70/90/100 response at each double-blind phase visit, a supplementary estimand (Estimand 6) will use the treatment policy strategy. It estimates the effect regardless of treatment adherence. It differs from the composite estimand ([Section 2.3.2.1](#)) in the following 2 attributes:

- Variable: aJIA ACR 30/50/70/90/100 response at each double-blind phase visit through Week 52.
- Intercurrent event: the intercurrent event of investigational product discontinuation will not be considered. More specifically, unlike Estimand 2, LOCF is not applicable and subjects who discontinue from investigational product will not be considered as ACR non-responders. All the aJIA ACR data collected while On- and Off-investigational product until Week 52 will be used to derive the endpoints.

For all secondary continuous endpoints in double-blind phase ([Section 3.2.1](#)), the estimand will use the hypothetical strategy (Estimand 7). It differs from the treatment policy estimand ([Section 2.3.2.2](#)) in the following 2 attributes:

- Variable: secondary continuous endpoints such as change from double-blind baseline in JADAS-27 CRP and JADAS-27 ESR at each scheduled visit through Week 52 in the double-blind phase.
- Intercurrent event: investigational product discontinuation will be the intercurrent event. All data after the intercurrent event, if collected, will be excluded; ie, only the on-treatment data ([Appendix 3.13](#)) will be used.

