### 5.3.2.1. Adapted JIA ACR30-50-70-90-100 Response

The Adapted JIA ACR30-50-70-90-100 responses will be derived programmatically and used in analyses. If the value in any of the components at a timepoint is missing, the component variables that are not missing will be used to determine the response status. As a general principle, if there are sufficient non-missing components to determine whether the ACR endpoint is a response or non-response, then ACR endpoint is not missing, else if the available non-missing components are not sufficient to determine the response status of ACR endpoint then it is considered missing.

Missing responses will not be imputed for descriptive summaries. For Estimand 2 and Estimand 6 analyses, missing responses will be handled as described in [Section 5.3.2](#).

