#### **6.2.1.3. Supplementary Analyses**

For aJIA ACR 30/50/70/90/100 response at each scheduled visit in the double-blind phase through Week 52, an additional analysis using the treatment policy estimand strategy ([Section 2.3.4](#)) will be performed. It will use the same methodology and summary as in [Section 6.2.1.1](#) but will also include data collected after the intercurrent events of investigational product discontinuation, ie, all data collected while On- and Off-investigational product until Week 52 will be used to derive the endpoints.

For all DB continuous secondary endpoints listed in [Section 3.2.1](#) (change from DB baseline in JADAS-27 ESR/CRP, change from both OL and DB baseline in each sJIA ACR core variable, change from DB baseline in CHQ responses and CHAQ discomfort index), an analysis using the hypothetical estimand strategy (Section 2.3.4) will be performed. It will use the same methodology and summary as in [Section 6.2.1.2](#) but only the on-treatment data ([Appendix 3.13](#)) will be used.

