**Table 4. Summary of Efficacy Analyses**

Endpoint	Estimand and Analysis Type	Population	Data Inclusion and Rules for Handling Intercurrent Events and Missing Data	Analysis Model
			Missing data are not imputed, assuming censoring at random.	
Adapted JIA ACR responses by DB visit	Secondary estimand	DBFAS	For investigational product discontinuation due to study end and end of study treatment after clinical remission, use last ACR value before discontinuation. Investigational product discontinuation for any other reason are treated as non-response.	Normal approximation
	Estimand 2 Composite Strategy  Secondary analysis		Missing responses are treated as non-response.	
	Estimand 6 Treatment Policy Strategy  Supplementary analysis	DBFAS	The intercurrent event of investigational product discontinuation will not be considered. All the data collected while On- and Off-investigational product until Week 52 will be used to derive the endpoints.  Missing responses are treated as non-response.	Normal approximation

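### In supplementary Estimand 6 (treatment-policy ACR response), children who complete in clinical remission and visits falling after study end are scored as non-response

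*SAP*

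**What the plan says.** Estimand 2 (SAP 2.3.2.1) is the main estimand for ACR response. It carries the last on-treatment value forward to Week 52 for two groups: children who complete after 24 weeks of inactive disease, and "patients who are still active in the double-blind withdrawal phase of the study but have to discontinue before Week 52 due to study end".

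Estimand 6 (SAP 2.3.4) is the supplementary treatment-policy version. There, "unlike Estimand 2, LOCF is not applicable and subjects who discontinue from investigational product will not be considered as ACR non-responders". SAP 6.2.1.3 adds that "all data collected while On- and Off-investigational product until Week 52 will be used to derive the endpoints".

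For what is still missing, SAP 5.3.2 says "any remaining missing responses will be handled by setting the response value to nonresponsive for visits up to DB Week 52". SAP 5.3.2.1 names the estimand: "For Estimand 2 and Estimand 6 analyses, missing responses will be handled as described in" Section 5.3.2. The Estimand 6 row of Table 4 (SAP Appendix 1) repeats it: "Missing responses are treated as non-response".

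SAP 2.2 and Protocol 6.8 end a child's participation in A3921165 at clinical remission. Follow-up of everyone else stops when the study concludes.

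**The concern.** A treatment-policy analysis of ACR response should show how children fare whether or not they stay on product. Followed exactly, the plan instead turns two exits that are not failures into failures. One is the best outcome the trial recognises. The other is a calendar event.

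This sits badly with the rest of the SAP. Estimand 1 censors both groups as non-flare, Estimand 2 keeps them at their last response, and Estimand 6 itself says that stopping product does not make a child a non-responder. If Estimands 2 and 6 disagree, part of the disagreement may come from the missing-data rule rather than from treatment.

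**Working it through.** **Remission completers.** Table 6 in SAP Appendix 3.13 has 13 scheduled visits through Week 52 (Weeks 4, 8, ..., 52). SAP 5.3.2.3 counts the 24 weeks of inactive disease from double-blind Day 1, so the earliest remission exit is Week 24. Weeks 28 to 52, which is 7 of the 13 visits, then have no A3921165 data and become non-response. A later remission loses fewer visits. One later value is conceivable: the protocol's Schedule of Activities marks an ACR assessment at the 4-week follow-up visit. Protocol 6.9, however, limits efficacy assessments there to children who stopped before Week 24 for reasons other than flare.

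**Children cut off by study end.** Inputs:
- Placebo median 236 days and hazard ratio 0.36 (SAP 5.1, Protocol 10.1.1).
- 23 randomised in 225 weeks, then 0.315 per week up to 54 (Protocol 10.1.1).
- Analyses at 28 and 37 flares (SAP 5.1).

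Assumptions: exponential times, the first 23 entries spread evenly, closure at the moment the target flare occurs, no remission exits, and flare-free status standing in for ACR response.

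Weekly hazards are 7 × ln 2 / 236 = 0.02056 (placebo) and 0.36 × 0.02056 = 0.00740 (tofacitinib). The flare-free share at Week 52 is exp(−52 × 0.00740) = 0.6805 and exp(−52 × 0.02056) = 0.3433, a difference of 33.7 points.

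Expected flares by calendar week T are the sum over entry times e of 1 − ½exp(−0.00740(T−e)) − ½exp(−0.02056(T−e)). This gives 20.07 at week 262 and 39.96 at week 358. Protocol 10.1.1 places its 20-flare and 40-flare analyses at those weeks, so the model reproduces the plan's timeline.

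Solving for the SAP's targets, with u = T − e as a child's potential follow-up and S(t) as the flare-free share at t weeks:
- Estimand 6 rate = (share with u ≥ 52) × S(52).
- Carry-forward rate = average over entries of S(min(u, 52)).
- Children cut off while flare-free = sum of ½S(u) over entries with u < 52, for each arm.

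| | 28 flares | 37 flares |
|---|---|---|
| Study-end week | 300.9 | 340.4 |
| Randomised | 46.9 | 54 |
| Share with u ≥ 52 | 65.1% | 79.6% |
| Flare-free but cut off (tofacitinib + placebo) | 6.8 + 5.0 = 11.8 | 4.3 + 2.8, total 7.0 unrounded |
| Estimand 6 rates | 44.3% vs 22.3% | 54.2% vs 27.3% |
| Estimand 6 difference (unrounded rates) | 21.9 points | 26.8 points |
| Carry-forward rates | 73.3% vs 43.8% | 70.0% vs 37.6% |
| Carry-forward difference | 29.5 points | 32.4 points |

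**Direction of the remission part.** Let shares r_t and r_p of flare-free children exit in remission. Under the proxy, the Week-52 difference among children with full follow-up is (1 − r_t) × 0.6805 − (1 − r_p) × 0.3433. This exceeds 33.7 points only if r_p / r_t > 0.6805 / 0.3433 = 1.98. Below that ratio it shrinks. Neither share is in the documents.

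**The case against.** **The rule is stated.** Non-response for missing data replaces carry-forward, and SAP 5.3.2.1 and Table 4 apply it to Estimand 6. A programmer has one answer. A reader might infer that the SAP contradicts itself or leaves these children without a rule. The text does not support that: SAP 2.3.4 handles the intercurrent event and 5.3.2 handles what is left. What stands is that the stated rule gives the wrong result for these two groups.

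**A3921145 data.** A reader might call their role in Estimand 6 an open ambiguity. For flare, SAP 2.3.3 says "the flare data collected through Week 52 post randomization from both studies A3921165 and A3921145 will be included". For ACR response the SAP is silent, and silence beside an explicit inclusion reads most naturally as exclusion. One clarifying line is enough.

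**The figures are rough.** Flare is judged against randomisation, whereas ACR response is judged against open-label baseline, so one proxy cannot serve five ACR thresholds. The design hazard also counts product discontinuation as flare, although such a child, if followed in the study, can be an ACR responder under Estimand 6. Closure will also lag the target flare. With an assumed 13-week lag, the 37-flare count falls from 7.0 to 4.1. The 28-flare count falls from 11.8 to 8.1 if accrual pauses and is unchanged if it continues. The 28-flare case arises only if the study stops at the First Analysis. These objections stand, and the figures are illustrative only.

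**Little depends on it.** This is also right, and it sets the severity.

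**Conclusion.** The point holds, at minor severity. Applied as written, Estimand 6 scores sustained remission and visits after administrative closure as treatment failure.

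The study-end part lowers the illustrative Week-52 difference by about 8 points (29.5 − 21.9 = 7.6) if the trial stops at 28 flares. At 37 flares it is about 6 points (32.4 − 26.8 = 5.6). Both rest on the proxy, the plan's own hazards and accrual, no remission exits and immediate closure.

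A reader might go further and infer that Estimand 6 is biased against tofacitinib by a known amount. The documents do not support this. They give no remission rates, and remission exits can shrink or enlarge the difference depending on the split between arms. Nor do the counts above settle whether most children complete 52 weeks, as SAP 2.3.2 and Protocol 10.2.2 expect. That depends on what completing means and is not part of this point.

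The primary analysis, Estimand 2, the treatment-policy analysis of the core variables (Estimand 3) and the unimputed descriptive rates are unaffected.

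**What to change.** For Estimand 6 only, amend SAP 2.3.4, 5.3.2, 5.3.2.1 and Table 4 before unblinding:

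- (a) Visits falling after administrative study end: exclude them from that visit's denominator, or multiply impute them, instead of scoring non-response.
- (b) Remission completers with no later data: replace automatic non-response with multiple imputation or Estimand 2's carry-forward, and report the other as sensitivity.
- (c) Keep non-response for all other missing data.
- (d) State in one line whether A3921145 ACR data to Week 52 are used. If they are, note that children who flare "will be given the opportunity to participate in A3921145 and be treated with open-label tofacitinib" (SAP 2.2), which would reduce the contrast. That study's visit schedule and ACR collection would also need checking, since neither is in these documents.

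The cost is a few SAP sentences and some programming, plus a specified imputation model if that option is chosen. Excluding visits leaves fewer children late on: about 15 per arm at Week 52 if stopped at 28 flares (46.9 × 0.651 / 2 = 15.3) and about 21 at 37 flares (54 × 0.796 / 2 = 21.5), before any remission exits. That thinning favours imputation for (a). No change to Estimand 2 is needed.

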### 5.3.2.1. Adapted JIA ACR30-50-70-90-100 Response

The Adapted JIA ACR30-50-70-90-100 responses will be derived programmatically and used in analyses. If the value in any of the components at a timepoint is missing, the component variables that are not missing will be used to determine the response status. As a general principle, if there are sufficient non-missing components to determine whether the ACR endpoint is a response or non-response, then ACR endpoint is not missing, else if the available non-missing components are not sufficient to determine the response status of ACR endpoint then it is considered missing.

Missing responses will not be imputed for descriptive summaries. For Estimand 2 and Estimand 6 analyses, missing responses will be handled as described in [Section 5.3.2](#).

### 5.3.2.2. JADAS-27 CRP, JADAS-27 ESR, and Occurrence of JADAS Minimum Disease Activity and Inactive Disease

For continuous measures (change from double-blind baseline in JADAS-27 scores), if any component is missing, then JADAS-27 CRP/ESR will be set to missing. These missing data will not be imputed otherwise and will be handled using the MMRM as described in [Section 5.2.3](#).

For binary assessments (occurrence of JADAS minimum disease activity and inactive disease), detailed definitions based on JADAS-27 CRP/ESR are in [Appendix 3.6](#). If JADAS-27 CRP/ESR value is missing, the corresponding binary assessments will be considered missing. Missing responses will not be imputed for descriptive summaries. For Estimand 2 analysis, missing responses will be handled as described in Section 5.3.2.

### 5.3.2.3. Presence of JIA ACR Inactive Disease and Clinical Remission

Calculations of JIA ACR inactive disease using ESR are as in [Appendix 3.7](#). If any of the components is missing, the components that are not missing will be used to determine the Clinical Inactive Disease Status as follows:

- Inactive disease: all components must be present (non-missing) and meet all conditions.
- Active disease: at least one component is present (non-missing) and does not meet the condition.
- Not determined: any other scenarios.

Clinical remission will be derived from inactive disease except when LOCF is applied in Estimand 2 as described in [Section 2.3.2.1](#). Clinical remission corresponds to at least 24 weeks of inactive disease continuously while on investigational product (for evaluation of this endpoint in the double-blind phase, the counting of 24 weeks starts from the double-blind phase Day 1).

### **5.3.3. JIA ACR Core Set Variables**

All JIA ACR Core Set Variables are continuous endpoints, missing data will be handled using the MMRM as described in [Section 5.2.3](#) and will not be imputed otherwise.

### **5.3.4. CHQ and CHAQ Responses**

CHQ and CHAQ responses are all continuous endpoints, missing scores will be handled using the MMRM as described in Section 5.2.3 and will not be imputed otherwise.

## **6. ANALYSES AND SUMMARIES**

### **6.1. Primary Endpoint: Time to Disease Flare in Double-Blind Withdrawal Phase**

#### **6.1.1. Primary Analysis**

- Estimand strategy: Composite ([Section 2.3.1](#)).
- Analysis set: DBFAS ([Section 4.1.1](#))
- Analysis methodology: Methods described in [Section 5.2.1](#) and decision rule in [Section 5.1](#) will be followed.
- Censoring time and risk period: On-Treatment Censoring Time and Risk Period ([Section 5.3.1.1](#)).
- Intercurrent events and missing data: See definitions described in Section 2.3.1 for intercurrent events; and [Section 5.3.1](#) for missing values.

